### 8.2.1 Total blood volume for laboratory assessments

Approximately 150 mL blood in total is collected from each subject during the entire trial period. Blood collection is performed in accordance with the guidelines in the EU Directive 2001/20/EC.

**Table 8–1 Volume of blood during the trial**

	Visit number												All visits
	V2	V3	V4	V5	V6	V8	V9	V10	V13	V16	V19	V20	
Total volume*	7.5	23.0	2.0	2.0	2.0	2.0	2.0	29.0	22.0	22.0	27.0	7.0	147.5 ml

*\*Precise volume at time of protocol preparation, minor variations may occur*

### 8.2.2 Laboratory reports

The central laboratory provides results to the trial sites in the units preferred by the trial sites while the results that are transferred to the trial database will always be in SI units.

Review of laboratory reports must be documented by the investigator (signed and dated) on the document. The evaluation of screening results must be dated and signed prior to randomisation (V3) and for the subsequent visits on the day of evaluation. For any laboratory result outside the reference range, it must be specified whether the value is clinically significant or not.

Protocol: Liraglutide  
Trial ID: NN8022-4179  
UTN: U1111-1162-7884  
EudraCT no.: 2014-004415-37

~~CONFIDENTIAL~~

Date: 16 July 2020  
Version: 5.0  
Status: Final  
Page: 47 of 125

**Novo Nordisk**

The laboratory equipment at the central laboratory may provide analyses not requested in the protocol but produced automatically in connection with the requested analyses according to specifications in the laboratory standard operating procedures. Such data will not be transferred to the trial database, but abnormal values must be reported to the investigator. The investigator must review all laboratory results for concomitant illnesses and AEs and report these according to this protocol.

The laboratory reports and evaluations must be retained as source documentation.

### **8.3 Subject related information**

#### **8.3.1 Demography**

The following information must be collected (according to local regulation):

- Date of birth
- Sex
- Race
- Ethnicity

#### **8.3.2 Concomitant illness and medical history**

A **concomitant illness** is any illness that is present at the start of the trial (V1) or found as a result of a screening procedure. All concomitant illnesses should be reported.

Any change to a concomitant illness should be recorded during the trial. A clinically significant worsening of a concomitant illness must be reported as an AE.

**Medical history** is a medical event that the subject has experienced in the past. Only relevant and significant medical history as judged by the investigator should be reported. The following medical history should be reported as a minimum if applicable: cardiovascular diseases, gallstone diseases (e.g. cholecystitis), pancreatitis and psychiatric disorders.

The information collected for concomitant illness and medical history should include diagnosis, date of onset and date of resolution or continuation, as applicable.

##### **8.3.2.1 History of psychiatric disorders**

Information related to psychiatric disorders (specifically history of depression, suicidal behaviour, anxiety, mood disorders, insomnia, or sleep disorders) must in addition to the medical history form also be recorded in the eCRF on a separate form.

Protocol: Liraglutide  
Trial ID: NN8022-4179  
UTN: U1111-1162-7884  
EudraCT no.: 2014-004415-37

CONFIDENTIAL

Date: 16 July 2020  
Version: 5.0  
Status: Final  
Page: 48 of 125

**Novo Nordisk**

### 8.3.3 Concomitant medication

A **concomitant medication** is any medication, other than the trial product, which is taken during the trial, including the screening and follow-up periods.

Details of any concomitant medication must be recorded at V2. Changes in concomitant medication must be recorded at each visit as they occur.

The information collected for each concomitant medication includes trade name or generic name, indication, start date and stop date or continuation. In addition, dose and route of administration for concomitant medication treatment for weight-related co-morbidities (diabetes mellitus, hypertension and dyslipidaemia) must be recorded.

If a change is due to an AE, then this must be reported according to section [12](#). If the change influences the subject's eligibility to continue in the trial, the monitor must be informed.

### 8.3.4 Tobacco use

Details of tobacco use must be recorded at V2.

Smoking is defined as smoking at least one cigarette, cigar or pipe daily. The collected information should include whether or not the subject smokes or has smoked.

If the subject smokes or has smoked, record approximately when the subject started smoking and, if applicable, when the subject stopped smoking.

## 8.4 Assessments for efficacy

The timing of the assessments are outlined in the flow chart (section [2](#)).

### 8.4.1 Body measurements

#### 8.4.1.1 Body weight

Body weight must be measured to the nearest 0.1 kg or 0.1 pounds. Fasting body weight must be measured at the fasting visits (section [8.1.2](#)). If the weight is not measured fasting at fasting visits, the subject must be called in for a new visit within the visit window to have the fasting weight measured. At the remaining visits the measurement is performed in a non-fasting state.

The same scale should be used throughout the trial. The scale must be calibrated according to the directions for use and as a minimum once a year.

Body weight should be measured without shoes and only wearing light clothing and the subject should have an empty bladder.

Protocol: Liraglutide  
Trial ID: NN8022-4179  
UTN: U1111-1162-7884  
EudraCT no.: 2014-004415-37

~~CONFIDENTIAL~~

Date: 16 July 2020  
Version: 5.0  
Status: Final  
Page: 49 of 125

**Novo Nordisk**

Body weight measured at V2 is used for the calculation of BMI to evaluate inclusion criteria. Body weight measured at V3 is used as baseline for assessment of change in body weight.

BMI is calculated in the eCRF.

#### **8.4.1.2 Hip and waist circumference**

The hip circumference is defined as the widest circumference around the buttocks.

The waist circumference is defined as the minimal abdominal circumference located midway between the lower rib margin and the iliac crest.

Three consecutive measurements each of hip and waist circumference must be performed. They should be measured in the horizontal plane and rounded up or down to the nearest 0.5 cm or 0.2 inches using a non-stretchable measuring tape.

The circumference should be measured when the subject is in a standing position wearing light clothing. At fasting visits the subject should be measured with an empty bladder. The subject should be standing, feet together with arms down their side and waist and hip accessible. The tape should touch the skin but not compress soft tissue and twists in the tape should be avoided. The subject should be asked to breathe normally and the measurement should be taken when the subject is breathing out gently.

The measurements should be performed in the following order: waist, hip, waist, hip, waist and hip. All three measurements must be recorded in the eCRF.

#### **8.4.2 Hyperphagia questionnaire**

Hyperphagia, a characteristic of patients with PWS, will be assessed using the hyperphagia questionnaire. The hyperphagia questionnaire has been developed for use in adults and children as young as 4 years of age with PWS, and has been recommended for use in this population by the 2014 2nd International Conference on Hyperphagia.

Hyperphagia is a significant source of stress for patients with PWS and their families, and can lead to complications including choking, and in extreme cases gastric rupture.

Liraglutide may influence hyperphagia through regulation of appetite. Liraglutide is known to increase feelings of fullness and satiety, while lowering feelings of hunger and prospective food consumption

The subject's LAR must fill out the PWS hyperphagia questionnaire according to flow chart (2).

Protocol: Liraglutide  
Trial ID: NN8022-4179  
UTN: U1111-1162-7884  
EudraCT no.: 2014-004415-37

~~CONFIDENTIAL~~

Date: 16 July 2020  
Version: 5.0  
Status: Final  
Page: 50 of 125

**Novo Nordisk**

### 8.4.3 Systolic and diastolic blood pressure

For blood pressure at V2, three measurements must be performed. The mean value is calculated by the eCRF and must be used to evaluate eligibility of the subject (exclusion criterion 19 and [Appendix B](#)). For the subsequent visits, only one measurement needs to be performed.

The method for measuring systolic and diastolic blood pressure should follow the standard clinical practice at site, but as a minimum, the following guideline must be adhered to:

- Caffeine, smoking and exercise at least 30 minutes prior to measuring the blood pressure should be avoided
- Blood pressure should be measured in a sitting position, with the legs uncrossed, the back and arms supported
- The subject should be sitting for at least 5 minutes before the first measurement is taken
- The subject should not talk during the measurement
- The same arm and cuff size should be used for blood pressure measurements at subsequent visits

Any “abnormal, clinically significant” findings at screening must be recorded as medical history/concomitant illness in the eCRF and in the subject’s medical record.

Any clinically significant worsening or new clinically significant findings after V2 must be reported as an AE in accordance with section [12](#).

If the investigator suspects white coat hypertension at V2, a re-assessment (three measurements) of the systolic and diastolic blood pressure is allowed, as described in exclusion criterion 19.

### 8.4.4 Blood samples for efficacy assessments

Any “abnormal, clinically significant” findings at V2 must be recorded as medical history/concomitant illness in the eCRF. The following blood samples must be drawn (for frequency see section [2](#)):

Lipids (fasting):

Protocol: Liraglutide  
Trial ID: NN8022-4179  
UTN: U1111-1162-7884  
EudraCT no.: 2014-004415-37

~~CONFIDENTIAL~~

Date: 16 July 2020  
Version: 5.0  
Status: Final  
Page: 51 of 125

**Novo Nordisk**

- Total cholesterol
- LDL-cholesterol
- VLDL-cholesterol
- HDL-cholesterol
- Triglycerides
- Free fatty acids
- Non-HDL cholesterol

Biochemistry:

- High sensitivity C reactive protein (hsCRP)

Glucose metabolism:

- HbA1c
- FPG
- Fasting insulin
- Fasting C-peptide

## 8.5 Assessments for safety

The timing of the assessments are outlined in the flow chart (section [2](#)).

### 8.5.1 Height

Height should be measured (centimetres or inches, one decimal) without shoes as two individual measurements performed by a single observer using identical technique with a Harpenden or other wall mounted stadiometer. The subject should be repositioned between the two measurements.

### 8.5.2 Hypoglycaemic episodes

At V3, all subjects and their LAR must be instructed in symptom recognition and handling of hypoglycaemia.

Blood glucose should always be measured and recorded when a hypoglycaemic episode is suspected.

All plasma glucose values:

- $\leq 3.9$  mmol/L (70 mg/dL) or
- $> 3.9$  mmol/L (70 mg/dL) when they occur in conjunction with hypoglycaemic symptoms

should be recorded by the subject or their LAR. These must be transcribed into the eCRF (hypoglycaemic episode form) throughout the trial from visit 3 to visit 18.

The record should include the following information:

Protocol: Liraglutide  
Trial ID: NN8022-4179  
UTN: U1111-1162-7884  
EudraCT no.: 2014-004415-37

~~CONFIDENTIAL~~

Date: 16 July 2020  
Version: 5.0  
Status: Final  
Page: 52 of 125

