Dietary counselling 8.7.2.1			x	x	x	x	x	x 	x 	x	x 	x 	x 	x 	x 	x 	x 	x 	x	x	x	x
Dietary compliance 8.7.2.1				x	x	x	x	x 	x 	x	x 	x 	x 	x 	x 	x 	x 	x 	x	x		
EFFICACY																						
Body weight 8.4.1.1		x	x	x	x	x	x	x	x	x	x	x	x	x	x	x	x	x	x	x	x	x
Waist and hip circumference 8.4.1.2			x	x	x	x	x	x	x	x	x	x	x	x	x	x	x	x	x	x		
Hyperphagia questionnaire 8.4.2			x							x									x			
Systolic and diastolic blood pressure 8.4.3		x	x	x	x	x	x	x	x	x	x	x	x	x	x	x	x	x	x	x		
Lipids 8.4.4			x							x		x	x			x			x			
hsCRP 8.4.4			x							x			x			x			x			
Glucose metabolism 8.4.4		x	x							x		x	x			x			x			
SAFETY																						
Height 8.5.1		x	x							x		x				x			x		x	x
Adverse events 12		x	x	x	x	x	x	x	x	x	x	x	x	x	x	x	x	x	x	x	x	x
Hypoglycaemic episodes 8.5.2 and SMBG 8.5.2.1			x	x	x	x	x	x	x	x	x	x	x	x	x	x	x	x	x			

Trial Periods	Screening	Screening	Randomisation	Dose escalation			Double blind treatment	Open-label treatment										End of treatment	Follow-up	TPD 16 week FU	TPD 52 week FU	
				4	5	6		7	8	9	10 	11	12 	13	14 	15 	16					17 
Visit number	1 	2 	3	4	5	6	7	8	9	10 	11	12 	13	14 	15 	16	17 	18 	19	20	10x	19x
Timing of visit (weeks)	-2		0	1	2	3	4	8	12	16	20	24	28	32	36	40	44	48	52	54	16	52
Visit window (days)				±2	±2	±2	±2	±5	±5	±5	±5	±5	±5	±5	±5	±5	±5	±5	±5	-5	±5	±5
Pulse 8.5.3		x	x	x	x	x	x	x	x	x	x	x	x	x	x	x	x	x	x			
ECG 8.5.4		x								x									x			
Pregnancy test  8.5.5		x 	x	x	x	x	x	x	x	x	x	x	x	x	x	x	x	x	x 			
First day of menstrual period 8.5.5.3			x	x	x	x	x	x	x	x	x	x	x	x	x	x	x	x	x	x		
Physical examination 8.5.6		x											x			x			x			
Biochemistry 8.5.7		x											x			x			x			
Haematology 8.5.7		x											x			x			x			
Hormones  8.5.7			x										x			x			x			

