Calcitonin 8.5.7		x											x			x			x			
Anti-liraglutide antibodies 8.5.8			x																x 	x 		
Tanner staging 8.5.9		x																	x 			
PHQ-9 and C-SSRS (part A only) 8.5.10		x																	x			
OTHER ASSESSMENTS																						
Liraglutide plasma concentration 8.7.1				x 	x 	x 		x 	x 	x 										x 		
TRIAL MATERIAL																						
Dispensing visit 9			x				x	x	x	x	x 	x 	x 	x 	x 	x 	x 	x 				
Drug accountability 9.4							x	x	x	x	x 	x 	x 	x 	x 	x 	x 	x 				

Trial Periods	Screening	Screening	Randomisation	Dose escalation			Double blind treatment	Open-label treatment								End of treatment	Follow-up	TPD 16 week FU	TPD 52 week FU			
				4	5	6		7	8	9	10 	11	12 	13	14 					15 	16	17 
Visit number	1 	2 	3	4	5	6	7	8	9	10 	11	12 	13	14 	15 	16	17 	18 	19	20	10x	19x
Timing of visit (weeks)	-2		0	1	2	3	4	8	12	16	20	24	28	32	36	40	44	48	52	54	16	52
Visit window (days)				±2	±2	±2	±2	±5	±5	±5	±5	±5	±5	±5	±5	±5	±5	±5	±5	-5	±5	±5
IV/IWRS session 10	x		x				x	x	x	x	x 	x 	x 	x 	x 	x 	x 	x 	x 			
New dose of trial product 8.1.7				x	x	x	x															
REMINDERS																						
Training in trial product & pen handling (including injection technique) 8.1.6			x	x	x	x	x	x	x	x	x 	x 	x 	x 	x 	x 	x 	x 				
Hand-out and instruct in BG meter 8.5.2.1			x																			
BG meter finger prick test 8.5.2.1			x	x	x	x	x	x	x	x	x	x	x	x	x	x	x	x	x			
Dispense dosing diary 8.7.3.1			x																			
Collect dosing diary				x	x	x		x	x	x												
Dispense hypoglycaemic episode diary 8.7.3.2			x																			
Collect hypoglycaemic episode diary				x	x	x	x	x	x	x	x	x	x	x	x	x	x	x	x			

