### **8.5.2.1 Self-measured blood glucose (SMBG)**

At V3, subjects are provided with a blood glucose (BG) meter including BG meter auxiliaries and instructions for use. The subjects or their LAR will be instructed in how to use and calibrate the device, according to the manufacturer's instructions. Instruction will be repeated as necessary during the trial.

The BG meters use test strips calibrated to plasma values. Therefore, all measurements performed with capillary blood are automatically calibrated to plasma equivalent glucose values, which will be shown on the display.

At each visit, the subject or subject's LAR must demonstrate how to use the BG meter device by measuring the subject's blood glucose value, preferably by using the subject's own BG meter. The SMBG value must be documented in the subject's medical record.

During dose escalation the SMBG measurement must be done before instructing the subject in dose escalation (section [8.1.7](#)). In case the value fulfils the criteria of a hypoglycaemic episode this must be recorded in the eCRF (section [8.5.2](#)).

Subjects or their LAR must be instructed to do a SMBG in between visits in case a hypoglycaemic episode is suspected (section [8.5.2](#)). The subjects must be instructed to contact the investigator in case of low SMBGs.

Subjects or their LAR should be instructed in how to record the results of the SMBGs in the diaries. The record of each SMBG should include date, time and value (section [8.7.3.2](#)). All hypoglycaemic episodes from the diary must be transcribed into the eCRF.

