#### **8.7.3 Subject diary**

Subjects will be provided with a paper diary to be completed at home. Only the subjects and/or the LAR must enter data in the diary. Subjects will be instructed by the investigator in when and how to complete the diary. It is important to explain to the subjects the necessity of accurate diary recording.

Review of diaries must be documented by the investigator, either on the documents and/or in the subject's medical record. If clarification of entries or discrepancies in the diary is needed, the subject must be questioned and a conclusion made in the subject's medical record. Care must be taken not to bias the subject and it is important to explain to the subjects the necessity of accurate diary recording.

All data from the diary must be transcribed into the eCRF.

The diary will include three different sections as specified in sections [8.7.3.1](#), [8.7.3.2](#) and [8.7.3.3](#)

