### Classification of Hypoglycaemia:

Treatment emergent: Hypoglycaemic episodes will be defined as treatment emergent if the onset of the episode occurs on or after the first day of trial product administration, and no later than 14 days after the last day on trial product.

Nocturnal hypoglycaemic episodes: Are episodes occurring between 00:01 and 05.59 both inclusive.

Hypoglycaemic episodes are classified according to the Novo Nordisk classification of hypoglycaemia and the American Diabetes Association (ADA) classification of hypoglycaemia (see [Figure 17-1](#)).

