**Table 4-2 Overview of defined analysis set**

Defined Analysis Data Sets	Description
In-trial	
The time period where the subject is supposed to be in the trial. The in-trial period begins at date of first dose of trial product and ends at the date of:
 
 
• The last direct subject-site contact, which is planned to take place at a follow-up visit
 
• Withdrawal date for subjects who withdraw informed consent
 
• The last subject-investigator/site contact as defined by investigator for subjects who are lost to follow up
 
• Date of death for subjects who die before any of the above
 

On-treatment
	
The time period where subjects are treated with trial product. The on-treatment period begins on the date of first dose of trial product and at the earliest date of:
 
 
• The follow-up visits (subjects with trial product discontinued)
 
• Last day on trial product + 14 days
 
• Last study visit (early withdrawn subjects without FU visit).
 
 
On-treatment period is defined for Liraglutide 3.0 mg as week 0-52 and for Placebo week 0-16.

Double blinded
	
The double blind period is from first dose of trial product to week 16 (0-16).
 
For the events occurring in double blinded period (AE and Hypoglycaemic episode)
 
 
• For liraglutide double blinded period will be from (week 0) to (week 16)
 
• For placebo double blinded period will be from (week 0) to (week 16 + 14 days)
 

Open label
	
The open label period is of duration 36 weeks that is from end of week 16 to week 52.
 
For the events occurring in open label period (AE and Hypoglycaemic episode)
 
 
• For Liraglutide open label period will be from (end of week 16) to (52 weeks + 14 days)
 
• For placebo open label period will be from (end of week 16 +14 days ) to (week 52)
 

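### The protocol gives two end visits for collecting hypoglycaemic episodes (V18 and V19), and neither reaches the end of the liraglutide treatment-emergent window at week 54

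*Protocol*

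**What the plan says.** Collection rules in the protocol:

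- Section 8.5.2 requires glucose values and episodes to be entered on the hypoglycaemic episode form "throughout the trial from visit 3 to visit 18". The same section asks for a form for each episode, and adds an AE form and safety information form only when the episode meets SAE criteria.
- In the flow chart (section 2), the row "Hypoglycaemic episodes" (with SMBG) is marked from V3 to V19, and the row "Collect hypoglycaemic episode diary" from V4 to V19. Both are blank at V20. Section 8.5 refers to the flow chart for the timing of safety assessments.
- Section 8.5.2.1 states: "All hypoglycaemic episodes from the diary must be transcribed into the eCRF". Section 8.7.3 states: "All data from the diary must be transcribed into the eCRF". Neither sets an end visit.

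Analysis windows:

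- Protocol section 17.4.1.2 counts an episode as treatment emergent if its onset is "no later than 14 days after the last day on trial product".
- SAP Table 4-2 says of hypoglycaemic episodes and AEs: "For Liraglutide open label period will be from (end of week 16) to (52 weeks + 14 days". In the same table the placebo double-blind event window closes 14 days after week 16, and its open-label window runs from there to week 52.
- SAP section 5.4.1.3 summarises hypoglycaemia in trial, on treatment, and for the double-blind and open-label periods.

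SAP Appendix 2, which lists changes to the planned analyses, does not mention the end visit.

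**The concern.** One safety assessment has three different end points: week 48 in section 8.5.2, week 52 in the flow chart, and week 54 in the analysis definitions. A site that follows 8.5.2 to the letter stops entering episodes while liraglutide subjects are still being dosed. A site that follows the flow chart stops two weeks before the treatment-emergent window closes.

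Severe episodes and blood-glucose-confirmed symptomatic episodes are listed safety endpoints (protocol section 4.2.2.3). They are reported as subjects with an event and numbers of events. AEs also get a rate per 1000 years, but hypoglycaemia has no exposure denominator. Any week without collection can therefore only lower the count, and nothing in the table would show it. A confirmed symptomatic episode that is not serious has the episode form as its only prescribed route into the database.

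**Working it through.** **Inputs.** SAP Table 6-2 gives the scheduled days: V18 is day 337, V19 day 365 and V20 day 379. Protocol Table 17-2 plans 38 liraglutide and 19 placebo subjects. Protocol section 17.1 assumes 20% withdrawal by week 52.

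**Reproducing the schedule.** Day = 7 × week + 1.

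- V18: 7 × 48 + 1 = 337
- V19: 7 × 52 + 1 = 365
- V20: 7 × 54 + 1 = 379

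All three agree with Table 6-2. Week 52 plus 14 days is day 379, so the liraglutide window closes on the scheduled day of V20.

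**Gap at the end of the liraglutide window.**

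- Section 8.5.2 (V18): 379 − 337 = 42 days = 6 weeks
- Flow chart (V19): 379 − 365 = 14 days = 2 weeks

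**Share of each window uncovered** (completers on the nominal schedule):

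| Window | Length (weeks) | If collection ends at V18 | If collection ends at V19 |
|---|---|---|---|
| Liraglutide, treatment emergent (0 to 54) | 54 | 6/54 = 11.1% | 2/54 = 3.7% |
| Liraglutide, open label (16 to 54) | 38 | 6/38 = 15.8% | 2/38 = 5.3% |
| Placebo, treatment emergent (0 to 18) | 18 | 0 | 0 |
| Placebo, open label (18 to 52) | 34 | 4/34 = 11.8% | 0 |
| In trial, either arm (0 to 54) | 54 | 6/54 = 11.1% | 2/54 = 3.7% |

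The placebo treatment-emergent window is fully covered because V11, at week 20, still collects episodes.

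**Exposure in the gap, liraglutide arm.**

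- To V18: 38 × 42 / 365.25 = 4.4 subject-years, or 30.4 × 42 / 365.25 = 3.5 if 20% are lost
- To V19: 38 × 14 / 365.25 = 1.5 subject-years, or 30.4 × 14 / 365.25 = 1.2 if 20% are lost

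**Reading the rules together.** For weeks 48 to 52, section 8.5.2 says stop, while the flow chart and sections 8.5.2.1 and 8.7.3 say continue. That is a contradiction between instructions. For weeks 52 to 54, the open-ended wording of 8.5.2.1 and 8.7.3 does not help in practice: the diary is last collected at V19, and V20 has no hypoglycaemia assessment.

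**The case against.** The best defence is that the flow chart governs. Section 8.5 defers to it for timing, and three further provisions (a form for each episode, all diary episodes, all diary data) set no end visit. On that view the visit number in 8.5.2 is a slip and weeks 48 to 52 are collected. This has force. A reader might infer that the last six weeks are lost, but the documents do not establish it.

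A reader might also infer that only the liraglutide arm is affected. That holds for completers' treatment-emergent window and for no other. Under the V18 rule placebo also loses open-label and in-trial time. Early discontinuers in either arm attend V20 two weeks after their V19 procedures (section 8.1.8), again with no hypoglycaemia row.

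Four further points count against overstatement:

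- The randomised, blinded comparison over weeks 0 to 16 is fully covered on every reading.
- The on-treatment windows differ by design (54 against 18 weeks), so those raw counts were never a like-for-like comparison, and no test is planned.
- Episodes meeting SAE criteria are also reported as AEs, which section 12.2 collects to the end of follow-up. They would reach safety reporting even if missing from the episode-form table.
- The on-treatment row of SAP Table 4-2 closes by giving weeks 0 to 52 for liraglutide, which the flow chart would cover. However, the same row allows 14 days after the last dose, and the table's event windows and protocol section 17.4.1.2 use the 14 days explicitly.

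What survives is the contradiction between V18 and V19 and the unscheduled two weeks after V19.

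**Conclusion.** The point holds as a mismatch between collection schedule and analysis window. Weeks 48 to 52 are under contradictory instructions, with up to 6 of 54 weeks (11.1%) of a liraglutide completer's treatment-emergent window uncovered if 8.5.2 is applied literally. Weeks 52 to 54, 2 of 54 weeks (3.7%), have no scheduled collection on any reading.

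These are shares of calendar time. The documents give no hypoglycaemia rate, so they cannot be read as shares of episodes missed, and the further inference that risk on liraglutide has been understated by a known amount is not supported. The direction is clear all the same: for completers, missing treatment-emergent weeks can only reduce the liraglutide count.

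The figures assume completers on the nominal schedule. The in-trial figures also assume that both arms attend V20. No primary or key secondary endpoint is affected. A listed safety endpoint is, so the passages should be reconciled.

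**What to change.** Change the end visit in section 8.5.2 to V20, and add V20 to the hypoglycaemia and diary-collection rows of the flow chart for all subjects. Covering both arms matters: the in-trial window runs to the last study visit in each, so adding V20 for liraglutide alone would make in-trial ascertainment unequal. The cost is a wording change and one more use of an existing form and diary at a visit that already collects AEs.

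The SAP already reports week 52 findings from blinded review in both parts, so collection may be complete or nearly so. If it is closed:

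- confirm with sites and data management that episodes up to V19 were transcribed;
- end the SAP hypoglycaemia windows at the last visit actually collected;
- state the end visit and the uncovered weeks in the clinical trial report.

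This route costs a data check and a few lines of SAP and report text.
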